4. STUDY POPULATION

4.1. Number of Subjects

Approximately 67 subjects will be enrolled to complete dosing and critical assessments. The subject numbers will be split to approximately 40 healthy volunteers and 27 patients with psoriasis.

Additional subjects/cohorts may be enrolled between the 0.0003mg/kg and 5mg/kg doses to allow for evaluation of additional dose levels but they will not exceed 5mg/kg (see Section 5.4).

If subjects prematurely discontinue the study, additional subjects may be enrolled as replacement subjects at the discretion of the Sponsor in consultation with the investigator.

4.2. Eligibility Criteria

Specific information regarding warnings, precautions, contraindications, adverse events, and other pertinent information on the GSK investigational product or other study treatment that may impact subject eligibility is provided in the Investigators Brochure [GlaxoSmithKline Document Number 2013N175515_01 and GlaxoSmithKline Document Number 2014N201916_00].

Deviations from inclusion and exclusion criteria are not allowed because they can potentially jeopardize the scientific integrity of the study, regulatory acceptability or subject safety. Therefore, adherence to the criteria as specified in the protocol is essential.

4.2.1. Inclusion Criteria

A subject will be eligible for inclusion in this study only if all of the following criteria apply:

- 1. Part A males aged between 18 and 65 years of age and Part B males and females aged between 18 and 75 years of age inclusive at the time of signing the informed consent.
- Part A: A body weight ≤120 kg and BMI within the range 19 32 kg/m2 (inclusive). For healthy volunteer subjects participating in Germany the BMI must be within the range of 19 – 30 kg/m2 (inclusive). Part B: BMI within range 19-35 kg/m² (inclusive).
- 3. **Part A only:** Healthy as determined by a responsible and experienced physician, based on a medical evaluation including medical history, physical examination, laboratory tests and 12-lead ECGs. A subject with a clinical abnormality or laboratory parameter(s) which is/are not specifically listed in the inclusion or exclusion criteria, outside the reference range for the population being studied may be included only if the Investigator in consultation with the GSK Medical Monitor, if required, agree and document that the finding is unlikely to introduce additional risk factors and will not interfere with the study procedures.
- 4. **Part A DTH cohort only:** Subjects with a history of BCG vaccination as evidence by either:
 - A BCG scar and verbal confirmation of BCG vaccination
 - Or documented medical history of a BCG vaccination with or without a BCG scar
- 5. **Part B only:** Subject has psoriasis covering BSA ≥3% as assessed at Screening and Day -1.
- 6. **Part B only:** Subject has had a confirmed diagnosis of chronic plaque-type psoriasis (without recent documented flare within 30 days prior to screening) for at least 6 months.
- Part B only: Subject has at least 2 stable plaques assessed at Screening and Day -1. One of a suitable size and in a site suitable for repeat biopsy, and one for index lesion PLSS scoring. Both must have a PLSS lesional score of ≥2 for the induration component (moderate or above), ≥1 for erythema and scaling with a total score of ≥5. The biopsy lesion must not be on the face, groin or scalp and must be protected from the sun.
- 8. Part A only: Subjects with a history of vaccination for Tetanus, diphtheria, measles, pertussis, mumps and rubella.
- 9. **Part B only:** A female subject is eligible to participate if she is not pregnant (as confirmed by a negative serum human chorionic gonadotrophin (hCG) test at screening and negative urine hCG test at Day -1 for FRP), not lactating, and at least one of the following conditions applies:
 - a. Non-reproductive potential defined as:

- Pre-menopausal females with one of the following:
 - Documented tubal ligation
 - Documented hysteroscopic tubal occlusion procedure with followup confirmation of bilateral tubal occlusion
 - Hysterectomy
 - Documented Bilateral Oophorectomy
- Postmenopausal defined as 12 months of spontaneous amenorrhea [in questionable cases a blood sample with simultaneous follicle stimulating hormone (FSH) and estradiol levels consistent with menopause (refer to laboratory reference ranges for confirmatory levels)]. Females on hormone replacement therapy (HRT) and whose menopausal status is in doubt will be required to use one of the highly effective contraception methods if they wish to continue their HRT during the study. Otherwise, they must discontinue HRT to allow confirmation of post-menopausal status prior to study enrolment.
- Reproductive potential and agrees to use a barrier method (male condom or female diaphragm) plus to follow one of the options listed in the Modified List of Highly Effective Methods for Avoiding Pregnancy in Females of Reproductive Potential (FRP) (see Appendix 5) from 28 days prior to the first dose of study medication and until completion of the follow-up visit.

The investigator is responsible for ensuring that subjects understand how to properly use these methods of contraception. The investigator or designee should remind the subjects of the need to comply with these requirements approximately monthly, either at study visits or by telephone call until the follow-up visit.

- 10. ALT, alkaline phosphatase and bilirubin ≤ 1.5 xULN (isolated bilirubin >1.5 xULN is acceptable if bilirubin is fractionated and direct bilirubin <35%).
- 11. Based on single or averaged QTc values of triplicate ECGs obtained over a brief recording period:

-QTcF < 450 msec

12. Capable of giving written informed consent, which includes compliance with the requirements and restrictions listed in the consent form, and has provided written informed consent.

4.2.2. Exclusion Criteria

A subject will not be eligible for inclusion in this study if any of the following criteria apply:

- 1. Received live vaccine(s) (attenuated or recombinant) within 4 weeks of Day 1 or plan to receive a live vaccination during the study until follow-up.
- 2. Subjects who have history of tuberculosis or have close family members with confirmed MTB infection or who are positive at screening by Quantiferon testing.

- 3. Subject is unable to abstain from travelling to areas with high endemic rates of infectious diseases until the end of the follow up period.
- 4. A medical history of severe allergic reaction, angio-edema, anaphylaxis or immunodeficiency.
- 5. Subjects with neutrophil results below the normal range at screening and baseline.
- 6. Subjects with any clinical, even mild, GI upset such as, but not limited to, diarrhea or abdominal cramping during the previous week before dosing, as well as history of more chronic GI upset, e.g. IBS
- 7. Current evidence of ongoing or acute infection within 3 months prior to the first dose of study drug, such as:
 - Serious local infection (e.g. cellulitis, abscess)
 - Systemic infection (e.g. pneumonia, septicaemia, TB)
- 8. **Part A (only cohorts, 1-4 without DTH challenge, and DTH cohort 5) only:** Subjects who test positive for pre-existing ADA to GSK2831781 at screening.
- 9. History of malignancy.
- Current or chronic history of liver disease, or known hepatic or biliary abnormalities (with the exception of Gilbert's syndrome or asymptomatic gallstones). Part A only: Subjects with an aspartate aminotransferase and/or gamma glutamyltransferase level above the upper limit of normal at screening and/or baseline will be excluded.
- 11. History of regular alcohol consumption within 6 months of the study defined as:

an average weekly intake of >21 units for males or >14 units for females. One unit is equivalent to 8g of alcohol: a half-pint (~240 ml) of beer, 1 glass (125 ml) of wine or 1 (25 ml) measure of spirits.

- 12. History of sensitivity to any of the study medications or PPD challenge agent, or components thereof or a history of drug (or IgG therapeutic antibodies) or other allergy that, in the opinion of the investigator or GSK Medical Monitor, contraindicates their participation.
- 13. A positive pre-study Hepatitis B surface antigen or Hepatitis B core antibody, or positive Hepatitis C antibody result within 3 months of screening.
- 14. A positive pre-study drug/alcohol screen.
- 15. A positive test for HIV antibody.
- 16. Where participation in the study would result in donation of blood or blood products in excess of 500 mL within a 56 day period.
- 17. The subject has participated in a clinical trial and has received an investigational product within the following time period prior to the first dosing day in the current study: 3 months, 5 half-lives or twice the duration of the biological effect of the investigational product (whichever is longer).
- 18. Exposure to more than four new chemical entities within 12 months prior to the first dosing day.

- 19. **Part A (only cohort with DTH challenge) only:** Presence of tattoos, naevi or other skin abnormalities such as keloids (or a history of keloids) that may, in the opinion of the investigator, interfere with DTH assessments.
- 20. **Part A (only cohort with DTH challenge) only:** Use of nicotine patches on the arm at screening that would interfere with the injection sites.
- 21. **Part A (only cohort with DTH challenge) only:** Subjects participating, within seven days of screening, in recreational sun-bathing, or the use of a sun-bed, on the area of the skin from the wrist to the shoulder (inclusive).
- 22. **Part A only:** Use of prescription drugs or non-prescription drugs, if in the opinion of the investigator (in consultation with the GSK medical monitor), the medication will interfere with the study procedures or compromise subject safety.
- 23. **Part A only:** Subjects must not currently be taking any of the following: topical steroids on the arms, oral or systemic steroids or any other immune-modulators (the washout period will be determined, on a case by case basis, by the investigator in consultation with the GSK medical monitor).
- 24. **Part B only:** History of significant cardiac, endocrinologic, haematologic, pulmonary, metabolic, renal, hepatic, immunologic (excluding psoriasis and psoriatic arthritis), urologic, neurologic, dermatologic (except psoriasis), psychiatric or gastrointestinal conditions that, in the opinion of the investigator and/or GSK medical monitor, places the subject at unacceptable risk.
- 25. **Part B only:** Clinically significant abnormalities of laboratory assessments (not related to disease) as judged by the investigator and/or GSK medical monitor.
- 26. **Part B only:** All systemic psoriasis medications, including psoralen long-wave ultraviolet radiation treatments, or other systemic immunosuppressives, are not allowed within 5 half lives prior to Day -1 (Methotrexate and cyclosporin are not allowed within 8 weeks of Day -1; Psoralen long-wave UV is not allowed within 4 weeks of Day-1). Subjects should not be included if the investigator considers that the subject is at high risk of requiring rescue with prohibited medication (see Section 5.14.2.3) for duration of study up to follow-up. This assessment should be based on current disease activity or a history of frequent and/or severe flares requiring systemic immunosuppression.
- 27. **Part B only:** The use of single treatment phototherapy (ultraviolet B or self treatment with tanning beds) is not allowed within 14 days prior to Day -1.
- 28. **Part B only:** The use of topical therapies for psoriasis are not allowed with 7 days prior to Day -1 on the index lesion or biopsy plaque.
- 29. **Part B only:** Previous treatment with anti-TNF/IL-12/IL-23 or any other monoclonal antibodies is not allowed within 12 weeks prior to Day -1.
- 30. **Part B only:** Patients that require narrow therapeutic index medications from Screening to Follow-up.
- 31. Vulnerable subjects (e.g. person kept in detention).

- 32. Subjects who are not able to understand and communicate in the native language of the country where the study is conducted.
- 33. Subjects who work for the Sponsor or CRO.

4.3. Lifestyle Restrictions

4.3.1. Dietary requirements

Subjects must fast overnight before screening for the glucose blood test. If the subject has not fasted then they may return before baseline to have the glucose blood test taken.

4.3.2. Alcohol

Subjects will abstain from alcohol for 24 hours prior to each visit to the clinical unit. Additionally they should refrain from alcohol for 7 days after dosing. Thereafter an average weekly intake of <21 units alcohol.

4.3.3. Activity

Part A and B: Subjects will abstain from strenuous exercise for 48 hours prior to dosing and prior to each blood collection for clinical laboratory tests. Subjects may participate in light recreational activities during studies (e.g., watch television, read).

Part B: Subjects must not sunbathe or use a tanning device (e.g. sunbed or solarium) whilst taking the study medication and until Day 43. Subjects will be advised that when they are outdoors they should wear protective clothing (e.g. sun hat, long sleeves) and use a broad spectrum UVA/UVB sunscreen and lip balm (SPF \geq 30) when outdoors.

4.4. Screen and Baseline Failures

Screen failures are defined as subjects who consent to participate in the clinical trial but are never subsequently randomized. In order to ensure transparent reporting of screen failure subjects, meet the Consolidated Standards of Reporting Trials (CONSORT) publishing requirements, and respond to queries from Regulatory authorities, a minimal set of screen failure information is required including, but not limited to, Demography, Screen Failure details, Eligibility Criteria, and any Serious Adverse Events.

4.5. Withdrawal Criteria and Procedures

A subject may withdraw from study treatment at any time at his/her own request, or may be withdrawn at any time at the discretion of the investigator for safety, behavioural or administrative reasons.

Refer to Section 5.4 or planned dose adjustment and Section 5.5 for subject specific dose adaptation including Liver Chemistry and QTc.

Liver chemistry threshold monitoring criteria have been designed to assure subject safety and to evaluate liver event etiology (in alignment with the FDA premarketing clinical liver safety guidance). See Section 5.6.1 for details.

4.6. Subject Completion

A completed subject is one who has completed all phases of the study including the follow-up visit.

The end of the study is defined as the last subject's last visit (which will be a combined follow-up/surveillance visit or a surveillance telephone call if the subject has already completed Follow Up, as specified in Table 1).

5. STUDY TREATMENT

5.1. Investigational Product and Other Study Treatment

	Study Treatment			
Product name:	GSK2831781 Diluent		Placebo	
Formulation	50mM Na Acetate,	0.9% NaCl solution	Commercial saline solution	
description:	51mM NaCl, 0.05mM	containing 0.015% PS80		
	EDTA, 0.02%			
	Polysorbate 80, and			
	57mM Arginine at pH			
	5.5			
Dosage form:	Solution	Solution	Commercial saline solution	
Unit dose	100mg/mL		Saline Placebo	
strength(s)/Dosage		N/A		
level(s):	SD of 0.0003-5mg/kg			
Route/	IV over approximately 2		IV over approximately 2	
Administration/	hours	N/A	hours	
Duration:				
Dosing	Infuse over		Infuse over approximately 2	
instructions:	approximately 2 hours	N/A	hours via an infusion pump	
	via an infusion pump			
Physical	Clear or opalescent,	Clear, Colourless to pale	Commercial presentation	
description:	colourless, yellow to	yellow, sterile solution		
	brown liquid that is			
	essentially free from			
	particles.			
Manufacturer/	GSK Parma, Italy	GSK Parma, Italy	Supplied by site	
source of				
procurement:				

5.2. Challenge Agents

	Challenge Agent
Product name:	Challenge agent PPD
Formulation description:	Tuberculin PPD RT23
Dosage form:	Solution
Unit dose strength(s)/Dosage	ID 2TU / 0.04µg
level(s):	ID 10TU / 0.2µg
Route/	Part A DTH cohorts:
Administration/	1x ID injection/single dose
Duration:	

	Challenge Agent	
Dosing instructions:	Part A DTH cohorts:	
	1 x ID injection left forearm 1 x ID injection right forearm	
	Followed by 4x ID injection 28 days later:	
	2 x ID injection left forearm 2 x ID injection right forearm	
Manufacturer/	Staten Serum Institut	
source of procurement:		

5.3. Treatment Assignment

Subjects will be assigned to receive GSK2831781 or placebo in accordance with the randomisation schedule generated by Clinical Statistics, prior to the start of the study, using the validated internal software RandAll NG.

The randomisation schedule will be generated to account for the sentinel subjects. Where the first two subjects dosed for any given cohort will be randomised so that 1 subject will receive GSK2831781 and 1 subject will receive matching placebo. In Part B, the sentinel subjects will be required to be ADA negative and subsequent subjects will be stratified by ADA status (ADA negative or ADA positive) as applicable (see Section 3.1.2).

Eligible subjects will receive a unique subject number which will be assigned in chronological order. Once a subject number has been assigned to a subject, it cannot be reassigned to another subject.

Each subject scheduled to receive study drug will also receive a treatment allocation number when randomised. The treatment number will indicate if the subject is to receive the scheduled dose of GSK2831781 or placebo at each dosing occasion.

A description of the projected regimens based on available data is provided in the table below:

Regimen	Description	Ratio (Active:Placebo)
А	0.0003mg/kg GSK2831781 IV single dose	1:1
В	0.0015mg/kg GSK2831781 IV single dose	1:1
С	0.0075mg/kg GSK2831781 IV single dose	3:1
D	0.04mg/kg GSK2831781 IV single dose	3:1
E	0.15mg/kg GSK2831781 IV single dose	1:1 for HV DTH (ADA-) 3:1 for HV No DTH (ADA +)
F	0.5mg/kg GSK2831781 IV single dose	4:2 for psoriasis (ADA-) 2:1 for psoriasis (ADA+)
G	1.5mg/kg GSK2831781 IV single dose	6:3 for psoriasis
Н	5mg/kg GSK2831781 IV single dose	6:3 for psoriasis
Р	Placebo IV single dose	N/A

5.4. Planned Dose Adjustments

This protocol allows some alteration from the currently outlined dosing schedule, but the maximum single dose will not exceed 5 mg/kg (to ensure about a 2.2 fold ratio with regard to the exposure (AUC) observed at 30 mg/kg in the cynomolgus monkey GLP toxicity study). The maximum dose exceeds the highest dose without neutropenia findings in the investigative monkey study, but will only be assessed providing the extensive within study monitoring has shown no clinically relevant safety findings at the lower doses.

Safety/tolerability data monitoring and the decision to proceed to the next dose level of GSK2831781 will be made by the DEC, consisting of the Principal Investigators (or appropriate designees), GSK Medical Monitor, GSK Study Team Leader (either Clinical Investigator Lead [CIL] and/or Operations and Science Lead [OSL]), GSK CPMS representative, a GSK GCSP representative, GSK Statistician and an independent GSK expert on FTIH studies. The DEC may also call on *ad hoc* internal/external members with specific expertise. DEC meetings will have open and closed sections. During the open section, the Principal Investigators will be present to provide additional information on patient assessment if required, and the data will be blinded. In the closed section, the Principal Investigators will not be present and if required data will be presented in an

unblinded manner. A DEC charter will be agreed between GSK and the principal investigator before the first DEC meeting.

For healthy volunteer cohorts, once safety data up to 28 days post-dose has been collected in all subjects for that cohort, the DEC will review the safety/tolerability data (including trends in neutrophil counts), the available PK data and for the DTH cohort, the clinical DTH response (induration diameter), before proceeding to the next dose level (See Section 3.2.1). The DEC may also consider available biomarker/PD data (including immune cell phenotyping) in considering the escalation. Outcomes of DEC review include escalation to the next dose, stopping the escalation, switching escalation to psoriasis patients, altering the next dose level, altering the subject numbers in a cohort. If emerging PK data departs from prediction, outcomes may also include continuing dose escalation in healthy volunteers beyond the maximum of 0.15mg/kg up to a maximum duration of exposure above EC50 of approximately 6 months, if there are no other safety/tolerability findings or reduction of DTH response (See Section 3.2.1).

For the psoriasis cohorts, once safety data and clinical measures of response (PASI and PLSS) at 28 days post-dose have been completed for a minimum of 8 out of 9 subjects, and all subjects have completed dosing and the inpatient monitoring until Day 4, the DEC will review the safety/tolerability data (including trends in neutrophil counts), the available PK data and the clinical response (PASI and PLSS) before proceeding to the next dose level. The DEC may also review the other measures of clinical response and available biomarker/PD data (including immune cell phenotyping) in considering the escalation. Outcomes of DEC review include escalation to the next dose, stopping the escalation, altering the next dose level or altering the subject numbers in a cohort. Definition of significant change in PLSS and/or PASI or strong trends in clinical response, leading to stopping of dose escalation at same or one higher dose will be discussed in the DEC Guidance/Charter document.

Apart from stopping of the dose escalation, alterations to the planned dose levels and intervals between dose levels will be limited to the following. Other changes will require a substantial amendment:

- Reduction in the dose increment to the next dose level (based on higher exposure than predicted and/or safety data of clinical significance).
- Introduction of an additional dose level cohort between the current and next planned dose level (based on higher exposure than predicted and/or safety data of clinical significance).
- Replacement of the highest dose level in psoriasis cohorts with a lower dose than the scheduled starting dose for psoriasis cohorts

For both healthy volunteers and psoriasis patients, the DEC will ensure that data from the ongoing cohort as well as accumulated data from all previous cohorts is reviewed. Decisions may be modified if subjects on placebo have findings. The dosing schedule may also add cohorts to evaluate 2 additional dose levels. The study procedures for these additional subject(s) or cohort(s) will be the same as that described for other study subjects.

5.5. Dose Adjustment/Stopping/Monitoring Criteria

If one or more subject experiences an Serious Adverse Event (SAE) that can be reasonably attributed to GSK2831781, the dose escalation will be halted and no further subject will be dosed until a full safety review of the data has taken place. Relevant reporting and discussion with the DEC, (which must include the GSK medical monitor), relevant GSK personnel, and with the Ethics Committee and Regulatory Agency will then take place. If following the safety review a decision is made to restart dose escalation, this may be allowed after approval of a substantial amendment.

If two or more subjects experience a severe or significant non-serious AE that can be reasonably attributed to GSK2831781, the dose escalation will be halted and no further subject will be dosed until a full safety review of the study has taken place. Relevant reporting and discussion with the DEC (which must include the GSK medical monitor), relevant GSK personnel, and with the Ethics Committee and Regulatory Agency will then take place. If following the safety review a decision is made to restart dose escalation, this may be allowed after approval of a substantial amendment.

Events of note across the cohorts (unless otherwise stated) that will also result in the study being temporarily halted and reviewed by the DEC include:

NOTE: If any of the below occur in the single active subject in the first 2 healthy volunteer cohorts the study will also be reviewed by the DEC.

- 1. Infusion Reaction/Hypersensitivity: Infusion reactions requiring termination of infusion/dosing in 2 or more subjects.
- Cytokine Release Syndrome (CRS): Evidence of CRS leading to moderate clinical symptoms in 2 or more subjects, based on modified NCI-CTC Criteria (see Section 12.3, Appendix 3). Symptoms include: Headache, fever, chills/rigors, nausea, vomiting, diarrhoea, arthalgia, myalgia, hypotension.
- 3. Neutropenia (the following must be confirmed by repeat samples):
 - If one subject experiences neutrophil count $<1.5 \times 10^9/L$ for >7 days for the first 28 days for the first 2 healthy volunteer cohorts.
 - If one or more subjects experiences neutrophil count $<0.5 \times 10^9$ /L for >7 days
 - If 2 or more subjects experience neutrophil count $<0.5 \times 10^9$ /L for <7 days.
 - If 2 or more subjects experience clinically significant neutropenia for >7 days.
- 4. Infections: If one or more subjects experiences an infection SAE, regardless of initial assessment of causality.
- 5. Liver event in one or more subjects:
 - a Hy's law liver SAE as characterised by $ALT \ge 3xULN$ and total bilirubin $\ge 2xULN$ (>35% direct bilirubin*); or $ALT \ge 3xULN$ and INR** > 1.5 (*serum bilirubin fractionation should be performed if testing is available; if unavailable, withdraw subject (if $ALT \ge 3xULN$ and total bilirubin $\ge 2xULN$) and measure urinary bilirubin via dipstick.** INR testing not required per protocol and the

threshold value does not apply to subjects receiving anticoagulants). The study will be also put on hold if one subject experiences

- ALT \geq 5xULN.
- ALT ≥ 3xULN if associated with symptoms (new or worsening) believed to be related to hepatitis (such as fatigue, nausea, vomiting, right upper quadrant pain or tenderness or jaundice) or hypersensitivity (such as fever, rash or eosinophilia).
- ALT \geq 3xULN persists for \geq 4 weeks.

QTC criteria: if 2 or more subjects demonstrate

- QTcF > 500 msec or,
- QTcF increase >60 msec from baseline

This assessment is to be based on an average QTc value of triplicate ECGs. If an ECG demonstrates a prolonged QT interval, then obtain 2 more ECGs over a brief period of time and then use the averaged QTc values of the 3 ECGs to determine whether the subject should meet these criteria.

If safety findings are noted in the active subject in cohorts with a single active subject, the cohort may be expanded to a maximum cohort size of 6:3 (active:placebo) or the escalation stopped.

To enable appropriate investigation of potential issues, the DEC will review data prior to continued dosing, if any of the following occur:

- 1. PPD challenge; if one or more subjects experience persistent reduction of the PPD challenge for \geq 3 months after rechallenge.
- 2. Moderate or severe adverse events of the same nature (including infections) in 2 or more subjects in the same cohort which can be reasonably attributed to dosing with GSK2831781, within 28 days of dosing (Appendix 4 and specific criteria at individual subject level in Section 5.6).
- 3. For a cohort of patients with psoriasis, if 2 or more subjects in a dose cohort experience a worsening of their psoriasis symptoms which can be reasonably attributed to dosing with GSK2831781, which requires treatment with prohibited concomitant medication.

The above criteria will apply regardless of whether pharmacokinetics are less than the PK stopping criteria described in Section 5.7 and every effort will be made to take a blood sample at the time of the event for pharmacokinetics analysis in the presence of any of the above events.

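### Protocol 5.5 item 3 leaves a neutrophil count below 0.5 x10^9/L lasting exactly 7 days outside both count-based halting bullets, so the rule is not monotone in duration (minor)

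*Protocol*

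**What the plan says.** Section 5.5 lists events that bring a temporary halt and DEC review, counted across cohorts unless stated otherwise. Item 3 is neutropenia, with the condition that "the following must be confirmed by repeat samples". It has four bullets:

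- Bullet 1 applies to the first two healthy-volunteer cohorts only: one subject below 1.5 x10^9/L for more than 7 days.
- Bullet 2: "If one or more subjects experiences neutrophil count $<0.5 \times 10^9$ /L for >7 days".
- Bullet 3: "If 2 or more subjects experience neutrophil count $<0.5 \times 10^9$ /L for <7 days".
- Bullet 4: "If 2 or more subjects experience clinically significant neutropenia for >7 days". Item 3 gives no numeric threshold for clinical significance.

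Two broader rules open the same section and carry no minimum duration. One begins "If one or more subject experiences an Serious Adverse Event (SAE) that can be reasonably attributed to GSK2831781", the other "If two or more subjects experience a severe or significant non-serious AE that can be reasonably attributed to GSK2831781". Either stops escalation, and restarting requires a substantial amendment.

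Section 5.4 adds that at each decision "the DEC will ensure that data from the ongoing cohort as well as accumulated data from all previous cohorts is reviewed".

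**The concern.** Bullets 2 and 3 look intended to work as a pair: one subject suffices if the severe count is prolonged, and two are needed if it is short. With > in one and < in the other, the value 7 falls between them. A halting rule should not become harder to meet as the event gets longer, yet here 6 days in two subjects qualifies and 7 days in two subjects does not.

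The risk is the one the protocol singles out. Section 1.2.1 reports neutrophil decrease as the adverse drug-related finding in the GLP monkey study. Section 3.3.2.4 puts the 5 mg/kg dose at 1.7 times the highest dose without neutropenia in the investigative monkey study, and its AUC at 2 times the AUC at that dose, and it relies on within-study monitoring to justify going there. Bullets 2 and 3 are the part of that monitoring that needs only a confirmed count, with no causality judgement.

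**Working it through.** There is no stated figure to reproduce. The check is a truth table.

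**Inputs.** Let d1 and d2 be two subjects' days with confirmed counts below 0.5, and w1 and w2 their days of clinically significant neutropenia, with w ≥ d. Whole days are an assumption, because the protocol does not define how days are counted. From item 3:

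- Bullet 2 fires if max(d1, d2) > 7.
- Bullet 3 fires if both d1 < 7 and d2 < 7.
- Bullet 4 fires if both w1 > 7 and w2 > 7.

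**Step 1: completed durations, bullets 2 and 3.**

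| d1, d2 | Bullet 2 | Bullet 3 | Result |
|---|---|---|---|
| 6, 6 | 6 > 7: no | both below 7: yes | halt |
| 3, 7 | 7 > 7: no | 7 < 7: no | neither |
| 7, 7 | 7 > 7: no | 7 < 7: no | neither |
| 3, 8 | 8 > 7: yes | not needed | halt |

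Neither bullet fires exactly when the longer episode is 7 days. The missed pairs are (1,7), (2,7), (3,7), (4,7), (5,7), (6,7) and (7,7). Further 7-day subjects do not help: six subjects at 7 days, or durations of 3, 7 and 7, still meet neither bullet.

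**Step 2: real time.** Item 3 does not say that durations are judged only once episodes are over. Suppose the first episode has ended at d1 and the second subject's low count is confirmed while that episode is still under 7 days.

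- If d1 is 1 to 6, both durations are below 7 at that moment and bullet 3 fires, even if the second episode later reaches 7.
- If d1 is exactly 7, bullet 3 cannot fire on this pair, and bullet 2 fires only if d2 goes past 7.

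Counting order of occurrence, Step 1 leaves 6 × 2 + 1 = 13 missed sequences. Real-time reading removes the six with d1 of 1 to 6 and d2 of 7, so 13 − 6 = 7 remain: d1 = 7 followed by d2 of 1 to 7. Two overlapping episodes, both confirmed before either reaches 7 days, also fire bullet 3.

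**Step 3: add bullet 4.**

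- d = (7,7): w = (7,7) or (7,10) gives no halt; w = (10,10) halts.
- d = (3,7): w = (3,7) or (3,10) gives no halt on completed durations; w = (10,10) halts.

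**Step 4: change bullet 3 to ≤7.** If either duration exceeds 7, bullet 2 fires. Otherwise both are 7 or less and bullet 3 fires. No pair is missed.

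**Step 5: can 7 days arise?** Tables 7 and 9 schedule haematology on Days 4, 8, 11, 15, 18, 22, 25 and 29. Six pairs of those visits are 7 days apart (4–11, 8–15, 11–18, 15–22, 18–25, 22–29), before visit windows and repeat samples. The value can occur. How often is unknown.

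**The case against.** The strongest reply is that item 3 is a prospective rule, so the seven-pair list overstates what would be missed while the trial is running. That stands: Step 2 cuts the hole to a first episode that stopped at exactly 7 days.

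Second, bullet 4 would often catch the 7+7 case. Counts below 1.5 are followed until no longer clinically significant (Section 5.6.4), and a subject below 0.5 for 7 days would usually take more time to recover through the range above. This also stands, but bullet 4 rests on clinical judgement and needs more than 7 days in both subjects.

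Third, other routes exist:

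- Section 7.1.4 names blood dyscrasias among events that may be serious without hospitalisation, so one attributed case could stop escalation.
- Two attributed severe or significant AEs do the same.
- A later list in Section 5.5 requires DEC review before further dosing when two subjects in one cohort have like AEs of at least moderate intensity, attributed to drug and within 28 days of dosing.
- The DEC looks at neutrophil trends at each escalation.

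The first three need attribution, the third is also confined to one cohort, and the last waits for the escalation decision. They reduce the consequence without repairing the count-based rule.

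Fourth, two low samples 7 days apart normally bracket an episode longer than 7 days, which points to bullet 2. That is fair, and it is why visit spacing shows only that 7 days is possible. Finally, the DEC charter is not among the documents and might settle the boundary.

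A reader might infer that two subjects with week-long severe neutropenia would pass without a halt. The documents do not support that, given these routes. Nor do they support treating all seven pairs as missed in live operation.

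**Conclusion.** The boundary error is real and minor. At exactly 7 days below 0.5 x10^9/L, neither count-based bullet applies, so that part of the rule is weaker for a longer event. Its extent depends on the reading: any pair whose longer episode is 7 days if completed durations are used, or only a 7-day first episode followed by one of 7 days or less if the rule is applied as data arrive.

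This assumes whole-day counting, confirmation of the second subject's count before its day 7 in the real-time case, and no contrary text in the unseen DEC charter. No probability of occurrence is claimed. What would be missed is an automatic temporary halt with DEC review, in a setting where the DEC can still act by other means.

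**What to change.** In Section 5.5 item 3, change bullet 3 to ≤7 days. Given bullet 2, this is equivalent to saying two or more subjects with a confirmed count below 0.5 x10^9/L of any duration, which also removes the question of how days are counted. Leave bullet 2 at >7 days: changing it to ≥7 would close the hole too, but would add a halt for a single subject at exactly 7 days. Check that the DEC charter is consistent.

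The cost is one symbol, handled through the usual amendment approval (Section 10.2), with no extra samples, visits or subjects. The downside is a slightly higher chance of a temporary halt.
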